2 STUDY PURPOSE

The study of the Edwards FORMA Tricuspid Transcatheter Repair System is a multi-center, international, prospective, single arm, safety study to assess the safety and device performance of the Edwards FORMA Tricuspid Transcatheter Repair System in patients with clinically significant, symptomatic tricuspid regurgitation who are at high surgical risk for standard tricuspid repair/replacement.

Data collected in this clinical study will include safety and device performance of the investigational system as well as up to 3 year clinical outcomes. In addition, the data shall be used to obtain regulatory approval.

2.1 INTENDED USE

[figure not shown]
The Edwards FORMA Tricuspid Transcatheter Repair System is intended for treatment of subjects with tricuspid regurgitation who are at high surgical risk for standard tricuspid repair/replacement due to operative risks, long recovery time, and/or significant comorbidities.

[figure not shown]
2.2 PRIOR TESTING

A Report of Priors (Clinical Investigator's Brochure (CIB)) has been prepared for the Edwards FORMA Tricuspid Transcatheter Repair System. This document provides the prior testing conducted on the system components.

2.3 PRIOR CLINICAL STUDIES

[Redacted text block]

[Redacted text block]

[Redacted text block]

[REDACTED]

2.4 STUDY DEVICE

2.4.1 GENERAL DEVICE DESCRIPTION AND COMPONENTS

The Edwards FORMA Tricuspid Transcatheter Repair System (herein after referred to as the FORMA System) is comprised of four (4) different sub-systems as listed below (Table 3). A general device description is provided for all components of the FORMA System. Further detailed information such as materials, manufacturing, testing, etc. however, will be provided in the Clinical Investigator’s Brochure (CIB). The FORMA System is not currently commercially available.

The following table includes the device names and model numbers of the components that make up the FORMA System.

Table 3 – Device Names and Model Numbers

Product Name	Models
Edwards FORMA Tricuspid Transcatheter Spacer System	[REDACTED]
Edwards FORMA Tricuspid Transcatheter Introducer Sheath Set	[REDACTED]
Edwards FORMA Tricuspid Transcatheter Railing Delivery System	[REDACTED]
Edwards FORMA Tricuspid Transcatheter Retrieval System	[REDACTED]

2.4.2 EDWARDS FORMA TRICUSPID TRANSCATHETER SPACER SYSTEM:

[REDACTED]

2.4.2.1 Spacer Device

[REDACTED]

[Redacted text block]

[figure not shown]
[Redacted text block]

[Redacted text line]

[figure not shown]
[figure not shown]

[Redacted text block]

[Redacted text line]

2.4.2.2 Railing System

[figure not shown]

2.4.2.3 Locking Mechanisms

[Redacted text block consisting of approximately 10 lines of blacked-out content]

[figure not shown]

2.4.3 EDWARDS FORMA TRICUSPID TRANSCATHETER INTRODUCER SHEATH SET

[figure not shown]
[figure not shown]
[Redacted text block consisting of approximately 8 lines of blacked-out content]

[figure not shown]
[figure not shown]
[Redacted line of text]

2.4.4 EDWARDS FORMA TRICUSPID TRANSCATHETER RAILING DELIVERY SYSTEM

[figure not shown]

2.4.5 EDWARDS FORMA TRICUSPID TRANSCATHETER RETRIEVAL SYSTEM

[Redacted text block consisting of seven horizontal black bars of varying lengths, covering several lines of text.]

[Redacted text block consisting of five horizontal black bars of varying lengths, covering several lines of text.]

3 RISK ANALYSIS

A risk analysis has been conducted, in accordance with ISO 14971: “Application of risk management to medical devices”. The risks associated with this investigational device have been identified by performing Failure Mode and Effect Analysis (FMEA)/Risk Analysis. Risks have been proven minimized through appropriate design control, confirmed by bench testing, pre-clinical animal testing and clinical surveillance presented in the Clinical Investigator’s Brochure.

During the conduct of the clinical study, the existing risk control measures shall be reviewed to identify if other hazards have been introduced. If any new hazards were introduced by any risk control measures, the associated risk(s) shall be re-assessed and addressed.

3.1 POTENTIAL RISKS

The potential risks of use of the FORMA System are similar to those encountered with standard cardiac catheterization and use of anesthesia and have been listed in two categories below. First, there are the potential complications associated with the overall procedure including standard cardiac catheterization and the use of anesthesia. Second, there are the additional potential risks associated with the use of the FORMA System.

Estimated occurrence rankings of the potential risks are provided in the Sample Informed Consent Form in Appendix A.

Risks related to the overall procedure including standard cardiac catheterization and the use of anesthesia may include, but may not be limited to, the following:

- abnormal lab values;
- access site AV fistula or pseudoaneurysm;
- allergic reaction to anesthesia or to contrast media;
- anemia;
- angina;
- arrhythmia;
- bleeding;
- cardiovascular or vascular injury including perforation, obstruction, or dissection of valvular structures that may require intervention, including access sites;
- conduction system injury (defect) which may require replacement or implantation of a pacemaker (temporary or permanent);
- death;
- dyspnea (e.g., orthopnea);
- electrolyte imbalance;
- embolization including air, particulate, calcific material, or thrombus;
- exercise intolerance or weakness;
- fever;
- heart failure;
- heart murmur;
- hematoma;
- hemorrhage requiring transfusion or intervention;
- leaflet damage;
- hypertension/hypotension;
- infection, including septicemia and endocarditis;
- inflammation;
- myocardial infarction;
- pain or changes at the access site;
- paralysis;
- pericardial effusion/cardiac tamponade;
- permanent disability;
- pleural effusion;
- pulmonary edema;
- renal failure;
- renal insufficiency;
- reoperation;

- restenosis;
- retroperitoneal bleed;
- syncope;
- systemic peripheral ischemia/nerve injury;
- thromboembolic events, stroke, transient ischemic attack, clusters, or neurological changes;
- wound dehiscence, delayed or incomplete healing.

In addition to the risks listed above, additional potential risks associated with the use of the FORMA System may include, but may not be limited to, the following:

- cardiac arrest;
- cardiac dysrhythmias requiring replacement or implantation of a pacemaker (temporary or permanent);
- cardiac failure/low cardiac output;
- cardiogenic shock;
- chordal damage, rupture;
- deterioration of native valve (leaflet tear/tearing, leaflet retraction, leaflet thickening, leaflet stenosis, or other);
- device degeneration;
- device explants;
- device migration, malposition or embolization potentially requiring intervention;
- device thrombosis requiring intervention;
- emergency cardiac surgery;
- hemolysis;
- leakage around device;
- non-emergent reoperation;
- nonstructural implant dysfunction;
- papillary muscle damage;
- pneumothorax;
- pulmonary artery outflow tract obstruction;
- skin burn;
- structural deterioration (wear, fracture, calcification, shaft creep, or other);
- thromboembolism (permanent or transient pulmonary and/or neurological events);
- transvalvular flow disturbances;
- valvular regurgitation;
- ventricular or atrial wall damage, abrasion, or perforation;
- worsening of heart failure;
- worsening of valvular insufficiency.

There may be other risks that are unknown at this time. All safety events will be collected and reviewed throughout the entire study and follow-up period. The Investigators will be notified of any additional risks identified that could affect the health, safety or welfare of the study subjects.

3.2 RISK MANAGEMENT

All efforts will be made to minimize the identified risks by selecting Investigators, team members and study sites who meet the following criteria:

- Interventional Cardiologist - must be board certified (or equivalent), experienced with performing transcatheter heart valve repair and replacement, and skilled in percutaneous coronary interventions and structural heart interventions.
- Access Management Physician - must be board certified (or equivalent), experienced with access management (subclavian/axillary vein access) and right heart interventions.

There will be strong interdepartmental collaboration between interventional cardiology and cardiovascular surgery operators and a designated team of nurses, technicians and colleagues from supporting medical disciplines (e.g., anesthesiologist, echocardiographer, radiologist).

The procedural location is to be an operating room, catheterization lab or hybrid operating room with fluoroscopic and echocardiographic imaging capabilities.

All adverse events will be thoroughly reviewed by the Study Sponsor and Data Monitoring Committee. The Study Stopping Rules are outlined in Section 16.

3.3 BENEFITS

The clinical benefits of using the FORMA System for the treatment of tricuspid regurgitation are not known at the present time. There are no guaranteed benefits from participation in this clinical study and being treated with the investigational FORMA System.

Tricuspid valve repair with the FORMA System may result in one or more of the following benefits for subjects typically considered high risk for tricuspid repair or replacement: decrease in tricuspid regurgitation, acute alleviation of symptoms related to tricuspid insufficiency, and/or improved morbidity and mortality.

Information gained from the conduct of this study may be of benefit to other people with the same medical condition in the future as the indication for the system is expanded.

3.4 JUSTIFICATION

This study, is designed as a multi-center, international, prospective, single arm, safety study. This study is designed to assess the safety and device performance of the FORMA System in a controlled human population.

The treatments currently available for this patient population include palliative medical therapy and high-risk surgical replacement or repair of the tricuspid valve. Treatment with the FORMA System may enable patients with tricuspid regurgitation, to undergo tricuspid valve repair via a minimally invasive approach.

4 STUDY OBJECTIVES

The objective of this study is to assess the safety and device performance of the Edwards FORMA Tricuspid Transcatheter Repair System in patients with clinically significant, symptomatic tricuspid regurgitation who are at high surgical risk for standard tricuspid repair/replacement.

5 STUDY ENDPOINTS

5.1 PRIMARY ENDPOINT

The primary endpoint for the study will assess the all-cause mortality of the as treated cohort at 30 days compared to a literature derived Performance Goal based on high-risk surgical outcomes for tricuspid repair/replacement.

5.2 SECONDARY ENDPOINTS & CLINICAL OUTCOMES

The following secondary endpoints and clinical outcomes will also be assessed:

5.2.1 TECHNICAL SUCCESS ENDPOINT

Technical Success will be assessed at exit from procedure room and is defined as:

- Alive, with
- Successful access, delivery and removal of the delivery systems, and
- Deployment and correct positioning of the intended device, and
- No need for additional emergency surgery or re-intervention related to the device or access procedure

5.2.2 DEVICE SUCCESS ENDPOINT

Device Success will be assessed at 1 month, 6 months and annually and is defined as:

- Alive, with
- Original intended device in place, and
- No additional surgical or interventional procedures related to the device, and

- TR reduction (assessment made by change in EROA) compared to baseline and TV gradient ≤ 5 mmHg

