5.2.4 CLINICAL OUTCOMES

Clinical Outcomes will be assessed at 1 month, 6 months & annually and are defined as:

- Re-hospitalization rates for the underlying condition (heart failure)
- Re-intervention rates for the underlying condition (tricuspid regurgitation)
- Change in Tricuspid Regurgitation (assessment made by change in EROA) from baseline
- Change in peripheral edema as assessed by subject weight loss (kilograms) from baseline
- Change in NYHA Class from baseline
- Change in 6 minute walk test distance (meters) from baseline
- Change in Quality of Life as assessed by the SF-12 and KCCQ questionnaires from baseline

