7.2 INCLUSION CRITERIA

The Investigator has the responsibility of screening potential subjects to determine if the patients meet all the inclusion criteria. The following are requirements for entry into the study:

1. Signed and dated EC approved study consent form prior to study related procedures
2. Eighteen years of age or older
3. Clinically significant, symptomatic (NYHA Functional Class II or greater), tricuspid regurgitation (Stage D per 2014 AHA/ACC guidelines) requiring tricuspid valve repair or replacement as assessed by the Heart Team
4. Functional tricuspid regurgitation (e.g., EROA \geq 0.4 cm² or equivalent guideline directed value) as the primary etiology
5. NYHA Functional Class II or greater or signs of persistent right heart failure despite optimal medical therapy
6. Determined by the 'HEART Team' (a minimum of one Cardiologist, and one Cardiac Surgeon) to be at high surgical risk for tricuspid valve repair or replacement and the benefit-risk analysis supports utilization of the investigational device
7. Willing to attend study follow-up assessments for up to 3 years

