8.3 BASELINE EVALUATION

1. Informed consent will be obtained from all patients who have been determined to be eligible study candidates and agreed to participate in the study.
2. Medical History (includes 6-month prior heart failure hospitalization rate), Clinical Evaluation (includes vital signs, weight and height), Concomitant Medication and NYHA classification
3. Administration of Health Status Questionnaires (SF-12, KCCQ)
4. Administration of Six Minute Walk Test
5. Clinical Laboratory Tests -
 - a. The following lab tests shall be done within 30 days of the scheduled implant procedure:
 - i. Troponins and/or cardiac enzymes (CK-MB) - *MI within 30 days of the scheduled implant procedure is an exclusion from study participation*
 - b. The following lab tests shall be done ≤ 2 weeks before implant procedure:
 - i. Brain Natriuretic Peptide (BNP)
 - ii. CBC and platelet count
 - iii. Complete metabolic panel
 - iv. Liver panel
 - c. The following lab tests shall be done ≤ 48 hours before the implant procedure:
 - i. Estimated Glomerular Filtration Rate (eGFR) - *eGFR result of < 25 is an exclusion from study participation for patients not already receiving dialysis*
 - ii. β HCG for women who are not sterile or post-menopausal- *positive result is an exclusion from study participation.*
 - iii. PTT/aPTT or PT/INR
6. Standard 12-lead Electrocardiogram (ECG)
7. Comprehensive Echocardiograms (Transthoracic [TTE] and Transesophageal [TEE]), if required¹, (within 90 days of scheduled implant procedure) including but not limited to, annulus size, ventricular size, regurgitant assessment, jet location, mean PAP and LVEF. Analysis will be conducted by the Investigator and Sponsor to certify the subject is eligible for the study.
8. Computed Tomography (CT) (within 90² days of scheduled implant procedure), that captures the anatomy of the subclavian and axillary veins, superior vena cava,

¹ The primary purpose of the TEE is to confirm the ability to image the tricuspid valve and possible anchoring location during the index procedure as this is the method that is used intra-procedure. If the TTE can demonstrate that the imaging of the valve and possible anchoring location is adequate, the TEE requirement at the baseline evaluation may be waived.

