13.5 ADDITIONAL ENDPOINT ANALYSIS

All statistical analyses will be performed by Edwards Lifesciences. Subject data listings and tabular presentations of results will be provided. All clinically relevant baseline and follow-up variables will be tabulated. Descriptive statistics will be used for continuous variables (e.g., mean, standard deviation, sample size, minimum, and maximum) and frequency tables or proportions for discrete variables.

Kaplan Meier estimates will be performed at the pre-specified follow-up times to project the estimates for time-related safety endpoints. The rate of freedom from all-cause mortality at 6 month, 1 year, 2 years, and 3 years will be estimated in addition to the primary endpoint which is established at 30 days post procedure.

Echocardiographic data will be analyzed by a core laboratory. The improvement from baseline items will be presented as shift from baseline for each of the pre-specified follow-up periods. Subjects that are missing a baseline or follow-up values will be excluded from the analysis.

Subjects that undergo any type of repair or replacement procedure for the tricuspid valve will be excluded from the implant cohort analyses at the time of the re-intervention.

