4.3 Additional Endpoint Analysis

The following secondary endpoints and clinical outcomes will also be assessed

4.3.1 Technical Success (at exit from procedure room):

- Alive, with

- Successful access, delivery and removal of the delivery systems, and
- Deployment and correct positioning of the intended device, and
- No need for additional emergency surgery or re-intervention related to the device or access procedure

4.3.2 Device Success (at 1 month, 6 months & annually):

- Alive, with
- Original intended device in place, and
- No additional surgical or interventional procedures related to the device, and
- TR reduction (assessment made by change in EROA) compared to baseline and TV gradient $\leq 5\text{mmHg}$

4.3.3 Procedural Success (at 1 month):

- Device Success, and
- None of the following device or procedure related SAEs:
 - Life threatening bleeding
 - Major vascular or cardiac structural complications requiring intervention
 - Pericardial effusion requiring drainage or surgery (includes tamponade)
 - Stage 2 or 3 acute kidney injury (includes new dialysis).
 - Severe heart failure or hypotension requiring IV inotrope, ultrafiltration or mechanical circulatory support
 - Prolonged intubation > 48 hours

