4.4 Transthoracic Echocardiogram (TTE) Parameters

- RA Area (cm²)
- RV End Diastolic Area (cm²)
- RV End Systolic Area (cm²)
- RA Volume (ml)
- RVED Volume (ml)
- RVES Volume (ml)
- RV EF (%)
- TAPSE (cm)
- RV Free Wall Thickness (cm)
- TV Annular Area 2D (cm²)
- TV Annular Area 3D (cm²)
- TV mean gradient (mmHg)
- LV EF (%)
- TR Vena Contracta inflow (cm)
- TR Vena Contracta Short Axis (cm)
- PISA EROA (cm²)
- Tricuspid Regurgitant volume (ml)
- Tricuspid Regurgitant EROA 2D (cm²)
- Tricuspid Regurgitant EROA 3D (cm²)
- Tricuspid Regurgitant RF (%)
- Jet Area (cm²)
- TR Jet VTI (cm)
- Tricuspid Leaflet Motion
- Tricuspid Leaflet Thickening
- Thrombus
- Pericardial Effusion
- Non-Study Valves AS
- Non-Study Valves AR
- Non-Study Valves MR
- Overall baseline TR

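### Device Success counts any fall in EROA as TR reduction, so measurement noise alone would meet that component in about half of subjects

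*Protocol*

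**What the plan says.** Protocol 5.2.2 makes Device Success a composite assessed at 1 month, 6 months and yearly. The subject must be alive, still have the first device in position and have had no further device-related procedure, and must also show "TR reduction (assessment made by change in EROA) compared to baseline" with a tricuspid gradient of at most 5 mmHg. SAP 4.3.2 repeats this: "TR reduction (assessment made by change in EROA) compared to baseline and TV gradient". The synopsis, the definitions section and SAP 2.3.2 use the same wording. The gradient has a numeric limit; the EROA change has none.

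Protocol 5.2.3 makes Device Success a required element of Procedural Success at 1 month.

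Four other places bear on the point:

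- Protocol 7.2, criterion 4, offers an EROA of 0.4 cm² or more as an example of qualifying regurgitation, "or equivalent guideline directed value) as the primary etiology".
- Protocol 8.3 says of the baseline echocardiogram: "Analysis will be conducted by the Investigator and Sponsor to certify the subject is eligible for the study". Protocol 13.5 says of the endpoint data: "Echocardiographic data will be analyzed by a core laboratory".
- SAP 4.4 lists three EROA variables (PISA EROA, a 2D EROA and "Tricuspid Regurgitant EROA 3D") and does not say which decides Device Success.
- Protocol 5.2.4 has a separate outcome at each visit: "Change in Tricuspid Regurgitation (assessment made by change in EROA) from baseline".

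**The concern.** A rule that accepts a fall of any size can be met by measurement error. If the device did nothing, the follow-up reading would still lie below baseline about as often as above it. If subjects were admitted because that same baseline reading was high, regression to the mean would tilt the balance further towards a fall.

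This matters because Device Success has no control arm, hypothesis or performance goal, so its definition is all that gives the percentage meaning. A reader who sees a rate well above zero may credit the device with an effect, without knowing that the reference level for the EROA component is about 50% and not 0%.

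**Working it through.** The documents state no expected rate for Device Success, so there is no figure to reproduce. The sample size of 63 in Protocol 13.1 belongs to 30-day mortality and does not bear on this point.

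**Inputs from the documents.** Any fall passes (5.2.2, SAP 4.3.2). The entry value is 0.4 cm², as an example (7.2). The eligibility and endpoint readers differ (8.3, 13.5).

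**Assumptions, since the documents give no EROA distribution or repeatability.** True EROA is lognormal with mean/SD 0.6/0.25, 0.8/0.35 or 1.0/0.5 cm². Lognormal reading error is independent at the two visits, with CV 10%, 20% or 30%.

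**1. Inert device, no selection on the baseline reading.** Write log baseline = log T + e0 and log follow-up = log T + e1. The subject passes if e1 < e0. With exchangeable errors P = 1/2 at any CV.

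**2. Inert device, same reading selected at 0.4 cm² or more.** Simulation with 2 million subjects per setting gives 51–58%. A wider grid (between-subject CV 30–50%) gives:

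| Mean true EROA (cm²) | Pass rate, inert device |
|---|---|
| 0.8–1.2 | 50–54% |
| 0.6 | 52–58% |
| 0.5 | 54–61% |

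**3. Sensitivity.** If EROA is rounded to 0.01 cm² and ties do not count as a fall, the wider grid gives 48–60%; rounded to 0.1 cm², 29–50%. A background change unrelated to the device also moves the figure: at mean 0.9 cm² and CV 20%, a true 10% fall gives 63–66% and a true 10% rise gives 38–40%.

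**4. Can the rule still tell devices apart?** Take a true 30% fall. The subject passes if e1 − e0 < −ln 0.7 = 0.357. The SD of e1 − e0 is √(2 ln(1 + CV²)), which is 0.141, 0.280 and 0.415 for CV 10%, 20% and 30%. Without selection:

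- CV 10%: Φ(0.357/0.141) = 99%
- CV 20%: Φ(0.357/0.280) = 90%
- CV 30%: Φ(0.357/0.415) = 80%

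With selection on the same reading the simulated range is about 82–99%. The inert device gives 50–58%, so the two are distinguishable as rates.

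**5. What a margin does.** Take a required fall of 30%, for illustration only. Without selection an inert device passes with probability Φ(−0.357/SD), which is 1%, 10% and 20% at the three CVs; with selection, 1–24%. The price is that a true fall exactly equal to the margin passes only about half the time, by the symmetry in step 1. A true 50% fall passes with probability Φ(ln(0.7/0.5)/SD) = Φ(0.336/SD), which is 99%, 88% and 79%.

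**6. The entry value as cut-off.** Requiring a follow-up EROA below 0.4 cm² would pass an inert device in only 1–16%. But it would pass a true 50% fall in only about 38–77%.

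**7. Precision.** Using 63 subjects as an illustrative size and the Clopper-Pearson interval of SAP 3.1, 38 of 63 meeting the component (60%) has a 95% interval of 47–72%, which still includes 50%.

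**The case against.** The strongest reply is that the component works well enough as a rate and that the plan does not rely on it alone. Step 4 supports the first part. A reader might infer that Device Success cannot separate an effective device from an ineffective one; the arithmetic does not support that. On the second part, EROA change is its own outcome at every visit, SAP 3.1 gives means, medians, ranges and confidence intervals for continuous variables, and echocardiographic items are shown as shifts from baseline. The size of effect will therefore be visible.

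Two further replies also stand. The excess over 50% needs the endpoint baseline to be the very reading used for selection. The documents point to different readers, and 0.4 cm² is only an example, so the excess may be close to nil. And Device Success is one of several descriptive secondary endpoints; nothing in the documents makes it the main measure of performance, and no type I error is involved.

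A reader might also infer that half of all subjects would be Device Successes with an inert device. That does not follow: the 50% applies to the EROA component alone, and the composite also needs survival, device retention, no related procedure and an acceptable gradient. Nor do the documents show that different EROA methods would be used at the two visits. SAP 4.4 is a list of table variables, and the echo protocol (Appendix C) is named but its content was not available for this review, so it may fix the method or a margin.

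None of this supplies a threshold in 5.2.2 or SAP 4.3.2. Reporting continuous change does not alter how the success rates are counted.

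**Conclusion.** The point holds in limited form. As written, any fall in EROA satisfies the regurgitation component of Device Success, and through it of Procedural Success. Noise alone would meet that component in about 50% of subjects, or slightly more if the baseline reading is also the selecting one. This rests on no background change, errors that behave alike at both visits, and finely recorded EROA; the CV affects only the excess over 50%. The consequence is for interpretation: an individual success may be noise, and the uncontrolled rate looks better than it should. It is an improvement to consider, and the primary mortality analysis is unaffected.

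**What to change.** In SAP 4.3.2, with Protocol 5.2.2 aligned, count TR reduction only when the EROA fall exceeds a margin for measurement error. Fix the margin before data review, for example from the core laboratory's repeatability data, and name one EROA method to be used at baseline and follow-up. Report the any-fall rate beside it, with a note that about 50% is expected from noise alone. If Appendix C already sets a margin or method, cite it in both places instead.

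The 0.4 cm² entry example should not become the success cut-off. Besides the missed responders in step 6, a subject falling from 1.2 to 0.5 cm² would fail, while one admitted on an equivalent criterion with EROA already below 0.4 cm² would pass unchanged.

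The cost is wording and no new measurements. The SAP edit is simple; aligning Protocol 5.2.2 needs a written amendment under Protocol 17.6. The downside is a lower reported success rate, with some true responders falling short of the margin.
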